
Statistical Analyses

 For severe hypoglycaemic events during the On-therapy time period an additional recurrent event analysis will be performed in a manner similar to that done for MACE (see Section 7.1.2). As a sensitivity analysis, this will also be done for the On-treatment time period. It is recognized that sulfonylurea /insulin use may increase risk of hypoglycaemic events; hence the recurrent events analysis will be also be done stratified by baseline sulfonylurea/insulin use (yes, no). Summaries and analyses of eGFR will be based on values from scheduled visits computed using the protocol-specified formula based on the measured creatinine, including baseline local and Central lab creatinine data and post-baseline scheduled visit Central lab creatinine data. For change from baseline eGFR, treatment group comparisons will be done using a MMRM analysis as previously described using an On-treatment analysis. Due to the event-driven nature of the study, beyond Month 16 only summary statistics will be provided. In addition, eGFR will be categorically summarized by visit as Normal ≥ 90, Mild ≥ 60 to < 90, Moderate ≥ 30 to < 60, and Severe < 30. Shift tables of eGFR from baseline to post-baseline planned relative timepoints will be provided including a summary of the shifts to the most severe eGFR category determined post-baseline. 
Sensitivity analyses will be done using the protocol-specified equation and measured creatinine, including baseline and post-baseline scheduled visit Central lab creatinine data. These will include the MMRM analysis and the shift tables.

Model Results Presentation

 For time to event endpoints, p-values and estimates of hazard ratios and 95% confidence intervals (CIs) will be presented, along with Kaplan-Meier (KM) curves by treatment group. For change from baseline endpoints, least square means, 95% CIs and nominal p-values will be presented, along with plots of least square means vs time by treatment group.

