During the study a creatinine assay quality issue was reported by the central lab which resulted in artificially high values. In addition to creatinine results, eGFR values may have been affected. The central lab indicated that this issue was restricted to samples assayed between 01Oct2016 and 13Jan2017 for sites in a subset of countries. It is anticipated that approximately 5%-20% of creatinine results that were assayed during this time period may be artificially high. Summaries will be provided to allow the potential impact of this issue to be evaluated. In particular, four summaries will be rerun excluding all data with sample dates in the time frame 26Sep2016-13Jan2017 (inclusive) for sites in the following countries: Argentina, Canada, Mexico, Peru, US. The specified time frame represents the earliest and latest dates of affected samples based on data provided by the central lab. The four summaries will include those for potential clinical concern for creatinine and change from baseline creatinine, along with the two MMRM analyses for change from baseline eGFR.

The Requirement for the Mexican Ministry of Health will be composed of the following:

- Listing of non-serious AEs for subjects at Mexican sites (this is expected to only include non-serious AESIs and non-serious AEs leading to discontinuation of IP)
- Listing of clinical events and SAEs for subjects at Mexican sites
- Listing of SAEs for subjects at non-Mexican sites

Subject profile listings will be generated for the following subjects in the Safety population: subjects with AESIs, subjects with AEs leading to discontinuation of IP, subjects withdrawn from study, and subjects who died. The listings will include demography, disposition, medical/surgical procedures, medical history, medication, all reported AEs and SAEs, CV event, death, lab, and vital signs data.

Narratives will be generated for subjects in the Safety population experiencing SAEs, pregnancies, non-serious AEs leading to permanent discontinuation of IP, non-SAE deaths (if any), and the following non-serious AEs that did not lead to permanent discontinuation of IP, but which are of potential clinical importance: severe hypoglycaemic episodes (not meeting the definition of Serious as these are in the set of SAEs listed above), and hepatic events recorded on the Liver Events eCRF that met the

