11.2.1. Time and Events Table

Procedures ^{1,2}	Screening ³	Randomization ³ /Baseline (can be same day as Screening Visit)	Study Drug Check Phone Call (4-6 wks post rand.)	Clinic Visit Month 4 ± 18 days then every 4 months ± 18 days throughout the study	Unscheduled dose adjustment visit (if warranted)	Final study clinic visit ⁴ (or early withdrawal)	Follow up Phone Call 5 ± 1 weeks after last IP dose
Written informed consent	X						
Review of Inc/excl criteria	X	X					
Demography & directed medical history	X						
Assessment of MACE and micro-vascular events				X		X	
HbA1c	X ⁵			X		X	
Serum creatinine (eGFR)	X ⁵			X (alternate visits) ²		X	
Liver Function Tests (LFTs) ⁶		X		X (alternate visits) ²		X	
Record available information on most recent lipid assessment ⁷		X		X (annually)		X	
Genetic sampling ⁸		X					
Patient reported outcomes questionnaires ⁹		X ¹⁰		X (alternate visits) ²		X	
Key concomitant non-diabetes medication		X		X		X	X
Diabetes medication		X		X		X	X
Study drug reminder			X	X	X		
Physical examination ¹¹		X		X (alternate visits) ²		X	
SAEs, AEs of special interest, AEs leading to IP discontinuation		X	X	X	X	X	X
Pregnancy test ¹²	X	X					
Study drug dispense/compliance ¹³		X		X	X	X	

1. Subjects who discontinue investigational product should be handled as described in Protocol Section 4.4 and Section 4.5. and Table 2 .
2. Assessments at month 8, 16, 24 etc. will include patient reported outcomes questionnaires, serum creatinine (eGFR), LFTs and physical examination. Those at months 4, 12, 20 etc do not.
3. Screening and Randomization can occur at the same visit if all eligibility information is available. If Screening and Randomization occur at the same visit assessments should not be duplicated.
4. Once it is projected that the target number of MACE events will have been collected, a 3 month window will be defined for conducting the final, face to face visit.

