Assessment of MACE and micro-vascular events	X		X	X	X
HbA1c	X			X	X
Serum creatinine (eGFR)	X			X	X
Liver Function Tests (LFTs) ⁵	X			X	X
Record available information on most recent lipid assessment ⁶	X		X (annually)	X (annually)	X
Patient reported outcomes questionnaire ⁷	X				
Key concomitant non-diabetes medication	X	X	X	X	X
Diabetes medication	X	X	X	X	X
Physical examination ⁸	X			X	X
AEs leading to IP discontinuation	X				
SAEs, AEs of special interest,	X	X	X	X	X
Study drug compliance	X				

1. After subjects permanently discontinue IP, follow-up should continue on the 4-monthly schedule established at randomization.
2. Where a subject would have been scheduled to attend clinic at months 4, 12, 20, 28 etc after randomization, a telephone contact will be performed instead (with assessments as shown above).
3. Where a subject would have been scheduled to attend clinic at months 8, 16, 24, 32 etc after randomization, a clinic visit will be performed (with assessments as shown above).
If a subject who has permanently discontinued IP is unable to attend clinic then they will be contacted by telephone instead and the telephone contact assessments will be performed.
4. Once it is projected that the target number of MACE events will have been collected, a 3 month window will be defined for conducting the final, face to face visit.
5. Liver function tests: ALT, AST, alkaline phosphatase, bilirubin, GGT.
6. Lipid values (TC, LDLc, HDLc, Tg) to be recorded as available from routine clinical care annually. If results are unavailable, lipids tests are not to be performed for the study.
7. TRIM-D, EQ-5D and study specific questionnaire (details in Protocol Section 6.3).
8. See Protocol Section 6.2.7.

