11.4.3. Treatment States for lab and vitals data

Treatment State	Definition
On-treatment	If assessment date is after treatment start date & on or before treatment stop date. Study Treatment Start Date < Assessment Date ≤ Study Treatment Stop Date

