3.144	Summary of On-therapy Malignant Neoplasms by History of Malignancy at Baseline, SOC, HLT and PT	Safety	SOC, HLT and PT, #/% of subjects and # of events, event density
3.145	Summary of Mantel-Haenszel Analysis of On-therapy Malignant Neoplasms, Stratified by History of Malignancy at Baseline	Safety	
3.146	Summary of On-therapy and Post-therapy Liver Monitoring/Stopping Event Reporting	Safety	
3.147	Summary of On-therapy Hepatobiliary Laboratory Abnormalities	Safety	
3.175	Summary of Liver Function Tests of Potential Clinical Concern	Safety	
3.148	Summary of On-therapy and Post-therapy Other CV Events	Safety	Other CV event category, #/% of subjects and # of events, event density
3.149	Summary of On-therapy Other CV Events	Safety	Other CV event category, #/% of subjects and # of events, event density
3.150	Summary of Chemistry Values	Safety	
3.151	Summary of Change from Baseline Chemistry Values	Safety	
3.152	Summary of Chemistry Values of Potential Clinical Concern	Safety	
3.153	Summary of Change from Baseline Creatinine Values of Potential Clinical Concern by Baseline eGFR	Safety	baseline eGFR category (Normal \geq 90, Mild \geq 60 to $<$ 90, Moderate \geq 30 to $<$ 60, and Severe $<$ 30 ml/min/1.73m ²)

Table No.	Title	Population	Programming note
3.154	Summary of Chemistry Shifts From Baseline with Respect to Potential Clinical Concern	Safety	
3.155	Summary of Change from Baseline Creatinine Values of Potential Clinical Concern (Central Laboratory Data) by Baseline eGFR	Safety	baseline eGFR category (Normal ≥ 90 , Mild ≥ 60 to < 90 , Moderate ≥ 30 to < 60 , and Severe < 30 ml/min/1.73m ²)
3.156	Summary of eGFR	Safety	Only use computed values
3.157	Summary of Change From Baseline in eGFR	Safety	Only use computed values
3.158	Summary of MMRM Analysis for On-treatment eGFR (ml/min/1.73m ²) Change From Baseline (Baseline Data from Local or Central Laboratory, and Post-baseline Central Laboratory Data)	Safety	Only use computed values
3.159	Summary of MMRM Analysis for On-treatment eGFR (ml/min/1.73m ²) Change From Baseline (Central Laboratory Data)	Safety	Only use computed values
3.160	Summary of eGFR Categories	Safety	Only use computed values
3.161	Summary of Shifts from Baseline in eGFR	Safety	Only use computed values
3.162	Summary of Shifts from Baseline in eGFR (Central Laboratory Data)	Safety	Only use computed values
3.163	Summary of Vital Signs	Safety	BP and Heart Rate
3.164	Summary of Change From Baseline Vital Signs	Safety	BP and Heart Rate

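### The assay-fault rerun omits the eGFR category and worst-shift tables, and no modelled eGFR comparison uses creatinine collected after study drug is stopped

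*SAP*

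**What the plan says.** **Assay fault.** Section 9.2.1 reports that the central laboratory produced artificially high creatinine in samples assayed from 1 October 2016 to 13 January 2017, for sites in some countries, and that eGFR may be affected. It expects roughly 5% to 20% of results in that period to be too high. Four displays are to be repeated without samples dated 26 September 2016 to 13 January 2017 from Argentina, Canada, Mexico, Peru and the US: "The four summaries will include those for potential clinical concern for creatinine and change from baseline creatinine", plus the two eGFR MMRMs. These are Tables 3.176 to 3.179.

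Section 8.2.2 also plans eGFR by category at each visit and shift tables, "including a summary of the shifts to the most severe eGFR category determined post-baseline". These are Tables 3.160 to 3.162.

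**eGFR model.** For change in eGFR, Section 8.2.2 says "treatment group comparisons will be done using a MMRM analysis as previously described using an On-treatment analysis". Section 11.4.3 defines on-treatment laboratory data as "Study Treatment Start Date < Assessment Date ≤ Study Treatment Stop Date". The display list carries the same limit: "Summary of MMRM Analysis for On-treatment eGFR" opens the titles of 3.158, 3.159, 3.178 and 3.179.

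**Collection after stopping.** Section 11.2.2 marks serum creatinine at the discontinuation visit, the continuing clinic visits and the final visit. Where a month 8, 16, 24 or 32 visit was due, "a clinic visit will be performed (with assessments as shown above".

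**The concern.** A worst-post-baseline table keeps each subject's single most severe value. A falsely high creatinine gives a falsely low eGFR, and that reading can fix the subject's category whatever the later samples show. A mean largely averages such an error out. The plan reruns the means and leaves the extreme-value display as it is.

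The only modelled eGFR contrast stops at the last dose, although off-drug samples are scheduled at the months the model uses. If subjects stop because renal function is falling, and the fall shows only in samples dated after the stop date, the model never sees it. The MMRM handles what is missing as missing at random (Section 8.1.2).

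The two points meet. The only eGFR displays cleared of the affected window are On-treatment models, so off-drug eGFR appears only in displays that still contain that window.

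**Working it through.** The plan states no figure on this point, so there is none to reproduce. The check is a trace of the text against the display list, followed by illustrations of scale.

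**1. Which displays are cleared of the window**

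| Display | Table | Rerun |
|---|---|---|
| Creatinine of potential concern | 3.152 | 3.176 |
| Creatinine change of concern, by baseline eGFR | 3.153 | 3.177 |
| eGFR MMRM, local or central baseline | 3.158 | 3.178 |
| eGFR MMRM, central only | 3.159 | 3.179 |
| eGFR categories | 3.160 | none |
| eGFR shifts | 3.161 | none |
| eGFR shifts, central only | 3.162 | none |

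**2. Does Table 3.162 remove the fault?** No. Under Section 8.2.2 both shift tables take post-baseline creatinine from the central laboratory, which is where the fault lay. Table 3.162 changes only which baselines are allowed.

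**3. Do the rerun creatinine tables stand in for the shift tables?** Only partly. They flag creatinine above 159 µmol/L or above twice baseline (Section 11.8.1), and Section 9.2.1 adds 1.5 times baseline. The eGFR categories change at 90, 60 and 30. A subject just above a boundary can cross it on a rise that triggers none of those flags.

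**4. Scale of the affected batch (illustration)**
- Window: 26 September 2016 to 13 January 2017 inclusive = 110 days.
- Sampling: "Assessments at month 8, 16, 24 etc. will include patient reported outcomes questionnaires, serum creatinine (eGFR), LFTs and physical examination", so every 8 × 30.4375 = 243.5 days.
- Share of followed subjects with a scheduled sample in the window: 110 / 243.5 = 0.452, assuming evenly spread visits and follow-up throughout.
- Share with a falsely high value: 0.452 × 0.05 = 2.3% to 0.452 × 0.20 = 9.0% of subjects in the five countries. This applies the stated percentage, given by assay date, to the slightly wider sample-date window.

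**5. Effect on a worst-category shift rate (illustration).** Let s be the true shift rate and m the chance that a false value crosses a boundary. With g = (share with a false value) × m, the tabulated rate is s + (1 − s)g. Assume s = 15% and m = 25% to 100%:
- Low: 0.15 + 0.85 × 0.0226 × 0.25 = 15.5%.
- High: 0.15 + 0.85 × 0.0903 × 1 = 22.7%.

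If g is equal in both arms, the tabulated absolute difference is (1 − g) times the true one. Here g runs from 0.0226 × 0.25 = 0.6% to 9.0%. Counts may be visibly inflated, while the absolute arm difference shrinks by at most 9% within those countries.

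**6. The eGFR model against the visit schedule.** A Month 8 or Month 16 sample after the stop date is scheduled under Section 11.2.2, excluded under Section 11.4.3, and used in none of Tables 3.158, 3.159, 3.178 or 3.179. The 56-day extension that adverse events receive (Section 11.4.2) does not apply to laboratory data.

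**7. Possible understatement in the model (assumptions only).** Suppose an excess e of albiglutide subjects stop after a fall d that the model never sees and that persists to Month 16. The difference is then understated by about e × d: 0.01 × 10 = 0.10 to 0.03 × 15 = 0.45 ml/min/1.73m². With an assumed SD of 14 and 3,000 per arm, SE = 14 × √(2/3000) = 0.36, so this is about 0.3 to 1.2 SE. For the chosen inputs these are upper bounds, because falls already visible on treatment are partly recovered by the model. None of e, d, SD or n per arm is in the SAP.

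**The case against.** The case for leaving the plan alone has substance.

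- **Both choices are open and consistent.** Text and display list agree, so there is no contradiction. This stands.
- **Renal harm after stopping is not invisible.** Worsening renal function is an adverse event of special interest, with a relative risk and 95% CI for On-therapy and Post-therapy combined (Section 8.2.2; Table 3.039). The microvascular endpoint counts dialysis and transplant from randomization. Tables 3.156, 3.157 and 3.160 to 3.162 are not restricted to on-treatment values. This stands and narrows the gap to the modelled eGFR contrast.
- **The direction of bias is conditional.** A reader might infer that an On-treatment analysis necessarily favours albiglutide. The SAP does not support that. If a fall reverses off drug, On-treatment shows more harm and an all-observed fit would dilute it.
- **HbA1c and weight are handled the other way round (Section 8.1.2).** A reader might call this an inconsistency. Those are efficacy endpoints in the ITT population, while eGFR is a safety endpoint in the Safety population, so the contrast is only a precedent for reporting both.
- **No individual value is known to be false.** The SAP identifies an affected batch and an expected proportion. It would be wrong to say that known false values are retained.
- **Threshold displays are already rerun, and the shift tables carry no test.** Tables 3.176 and 3.177 do help, but the eGFR boundaries are different cut points (step 3). The absence of a test means that no planned inference is affected. It does not make the displayed counts right.
- **A false baseline acts the other way.** This is true, and the exclusion rule removes affected baselines as well.

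**Conclusion.** The point holds in a limited form.

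The rerun omits the eGFR displays that a single false value changes most, and the existing central-laboratory sensitivity version does not fill the gap. The fault has no stated link to treatment arm, so the expected result is inflated worst-category counts in both arms and a mild dilution of the difference, not a spurious arm effect.

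Separately, creatinine collected off drug enters no between-arm eGFR estimate. This could understate harm, but only if stopping is related to a renal decline that persists. The documents do not show that it is, and they do not support replacing the On-treatment model or ranking it below another. The weakness is that it is the only one.

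Neither effect can be sized from the SAP, which gives no eGFR SD, discontinuation rate or subject count by country. The figures in steps 4, 5 and 7 are illustrations that rest on the assumptions stated there.

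**What to change.** 1. Add Tables 3.160, 3.161 and 3.162 to the set rerun without samples dated 26 September 2016 to 13 January 2017 from the five countries. Show the reruns beside the full tables and not in their place: by the plan's own estimate 80% to 95% of the dropped results are sound, so the exclusion also loses some true worst values.
2. Add an eGFR MMRM on all scheduled Month 8 and Month 16 central-laboratory values regardless of drug status, reported beside the retained On-treatment MMRM.

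**Cost.** A few extra tables from data already collected, using an exclusion rule and a model already specified. Off-drug values may dilute a reversible on-drug effect, which the On-treatment table still shows. Coverage off drug will be incomplete, because subjects who cannot attend clinic are contacted by telephone without a creatinine sample (Section 11.2.2).

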8.3. Secondary Value Evidence and Outcomes Analyses

8.3.1. Overview of Planned Secondary Value Evidence and Outcomes Analyses

The secondary Value Evidence and Outcomes analyses will be based on the ITT population.

Table 8 provides an overview of the planned secondary Value Evidence and Outcomes analyses, with further details of data displays being presented in Section 11.15. Although not specified in the protocol, it was subsequently clarified in the Study Reference Manual and the eCRF Completion Guidelines that questionnaires were not to be completed after subjects discontinued study treatment; hence such data should not be entered into the eCRF and will be programmatically excluded from all summaries and analyses (but included in listings with corresponding flag). For the TRIM-D and EQ-5D, if one or more questionnaire responses are missing at a timepoint for a subject, then the corresponding endpoint score will be missing.

Table 8 Overview of Planned Secondary Value Evidence and Outcomes Analyses

Endpoints	Absolute							Change from Baseline						
	Stats Analysis			Summary		Individual		Stats Analysis			Summary		Individual	
	T	F	L	T	F	F	L	T	F	L	T	F	F	L
Patient Reported Outcomes														
TRIM-D- OC					Y			Y	Y (x2) [1]	Y	Y (x6)			
EQ-5D - OC				Y (x6)	Y			Y	Y (x2) [1]	Y				
TRIM-D - LOCF				Y	Y									
EQ-5D - LOCF				Y	Y									

NOTES :

- T = Table, F = Figure, L = Listing, Y = Yes display generated.
- Stats Analysis = Represents TFL related to any formal statistical analyses (i.e. modelling) conducted.
- Summary = Represents TFL related to any summaries (i.e. descriptive statistics) of the observed raw data.
- Individual = Represents FL related to any displays of individual subject observed raw data.

[1] Plots of raw means vs time and also adjusted means vs time.

8.3.2. Planned Secondary Value Evidence and Outcomes Statistical Analyses

Statistical Analyses
Endpoints

 • Change from baseline in TRIM-D total score [1] • Change from baseline in EQ-5D Visual Analogue Scale (VAS) score
Model Specification

 • For change from baseline TRIM-D total score and change from baseline EQ-5D VAS score, treatment group comparisons will be done using a MMRM analysis as previously described. Due to the event-driven nature of the study, beyond Month 16 only summary statistics will be provided. Summaries and analyses will exclude data assessed after subjects discontinue study drug. Summaries and analyses of change from baseline TRIM-D total score will exclude subjects not on diabetes medication at baseline.
Model Checking & Diagnostics

 • Refer to Section 11.12.
Model Results Presentation

 • For change from baseline endpoints, least square means, 95% CIs and nominal p-values will be presented, along with plots of least square means vs time by treatment group.

[1] Summaries and analyses of change from baseline TRIM-D total score will exclude subjects not on diabetes medication at baseline.

TRIM-D total score and change from baseline TRIM-D total score, along with score and change from baseline score for each of the five domains (Treatment Burden, Daily Life, Diabetes Management, Compliance, Psychological Health) will be summarized by visit. Summaries will exclude subjects not on diabetes medication at baseline.

EQ-5D responses for each of the five domains (Mobility, Self-Care, Usual Activities, Pain/Discomfort, Anxiety/Depression) will be summarized categorically by visit; EQ-5D VAS score and change from baseline VAS score will be summarized by visit.

9. OTHER STATISTICAL ANALYSES

9.1. Other Efficacy Analyses

9.1.1. Overview of Planned Other Efficacy Analyses

The other efficacy analyses will be based on the ITT population, unless otherwise specified.

Table 9 provides an overview of the planned other efficacy analyses, with further details of data displays being presented in Section [11.15](#).

Table 9 Overview of Planned Other Efficacy Analyses

Endpoints	Absolute								Change from Baseline							
	Stats Analysis			Summary		Individual			Stats Analysis			Summary		Individual		
	T	F	L	T	F	F	L	T	F	L	T	F	F	L		
CV																
Time to Stroke or TIA [1]	Y	Y		Y												
Time to TIA [2]	Y	Y		Y												
Concordance Between Investigator-Reported and Adjudicated Events				Y (x6) [3]			Y									
Lipids (total cholesterol(TC), low density lipoprotein cholesterol (LDLc), high density lipoprotein cholesterol (HDLc), triglycerides (Tg), nonHDLc) [4]				Y (x2) [5]												

NOTES :

- T = Table, F = Figure, L = Listing, Y = Yes display generated.
- Stats Analysis = Represents TFL related to any formal statistical analyses (i.e. modelling) conducted.
- Summary = Represents TFL related to any summaries (i.e. descriptive statistics) of the observed raw data.
- Individual = Represents FL related to any displays of individual subject observed raw data.

[1] Time to first occurrence of adjudicated stroke or TIA.

[2] Time to first occurrence of adjudicated TIA.

[3] Efficacy, MACE, Death, MI/UA, Stroke/TIA, Individual Endpoint Event.

[4] Assessed per routine clinical care.

[5] Standard and SI units.

For time to first adjudicated stroke or TIA and also for time to first adjudicated TIA, a Cox Proportional Hazards regression model with treatment group as the only covariate will be used; an estimate of the hazard ratio and 95% confidence interval will be presented, along with Kaplan-Meier (KM) curves by treatment group.

If significant drop-in of medications which have the potential to impact CV outcomes occurs, exploratory summaries and analyses may be considered.

